7.0 Study Withdrawal/Discontinuation

A participant may withdraw from the study at anytime through written or verbal communication with a member of the research team. If a study participant stops participating in the study, the person will be notified that his/her participation in the study will be discontinued. Once notified of withdrawal or discontinuation, the participant will be immediately removed from the study and no further research appointments will occur.

8.0 Statistical Considerations

For this project, we will be enrolling 36 participants (18 per arm). Fifteen participants has been previously identified as a sufficient sample size per treatment arm to calculate the sample size of a 90% powered main trial with a medium standardized difference⁴⁸. An additional six individuals (three per treatment arm) will be included to account for a 20% attrition rate during the course of the trial. This sample size is adequate to detect a large effect size with 76% power and 5% significance on a one-tailed independent t-test.

A flow diagram will be used to document recruitment, enrollment, and retention. Descriptive statistics will be used for adherence to treatment, and independent t-tests or Mann-Whitney U tests will be run for treatment credibility, expectancy, and satisfaction. For the preliminary efficacy calculations, an intent-to-treat approach will be used, with the expectation maximization (EM) approach to be used if justified by missing values analysis⁴⁹. Cohen's *d* effect size will be computed for the group difference and will be used to inform a definitive clinical trial.

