The same randomized pilot trial will be used to compare the intervention ($n = 18$) to the control ($n = 18$).

Outcomes: The primary outcome will be objective PM abilities, as measured by the Memory for Intentions Test (MIST)^{28,29}, which will be used to generate a preliminary effect size estimate for a future trial. A secondary outcome will be subjective PM abilities, as measured by the Perceived Deficits Questionnaire (PDQ) subscale³⁰.

Hypothesis: Compared to the control group, participants in the treatment group will exhibit an improvement in their PM abilities. In addition, the treatment group will endorse fewer PM difficulties.

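### The stated 76% power assumes no loss from the 36 enrolled; at the plan's own 20% attrition it is about 67% for completers, and the six extra participants cover 16.7% loss, not 20%

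*Combined protocol and SAP*

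**What the plan says.** Section 8.0 (Statistical Considerations) sets enrolment at 36, 18 per arm, in three steps.

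- A pilot-sizing rule: "Fifteen participants has been previously identified as a sufficient sample size per treatment arm".
- An allowance for loss: "An additional six individuals (three per treatment arm) will be included to account for a 20% attrition rate during the course of the trial".
- A power statement: "This sample size is adequate to detect a large effect size with 76% power and 5% significance on a one-tailed independent t-test".

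The same section plans an intent-to-treat efficacy analysis, "with the expectation maximization (EM) approach to be used if justified by missing values analysis". Section 7.0 says that after withdrawal or discontinuation "the participant will be immediately removed from the study and no further research appointments will occur". Under Aim 2 in Section 2.0, the Memory for Intentions Test (MIST) is the primary efficacy outcome, "which will be used to generate a preliminary effect size estimate for a future trial". No power figure for the number expected to remain after attrition appears anywhere.

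**The concern.** The second and third steps use the same six people in two ways. The attrition sentence treats them as replacements for participants who will be lost. The power sentence, which comes next, counts them as observed outcomes. Nothing labels the 76% as a no-attrition figure, so a reader will take it as the power of the trial as planned.

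If the between-group comparison is inconclusive, the reader will put the chance of having missed a large effect at 24%. Under the plan's own attrition that chance is higher. There is also a smaller question: whether adding 3 to 15 per arm really allows for a 20% loss.

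**Working it through.** **Inputs**

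- From Section 8.0: 18 enrolled per arm, 15 per arm as the target, 20% attrition, one-tailed 5% independent t-test, stated power 76%.
- From Section 4.0: 1:1 allocation.
- Assumed: d = 0.8 for a large effect. The plan gives no number; 0.8 is the conventional value and returns the stated power.

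**Power formula.** Exact noncentral t, with df = n1 + n2 − 2, noncentrality δ = d × √(n1·n2/(n1 + n2)), and power = P(T > the one-sided 5% critical value).

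*The plan's own figure.* With 18 + 18, δ = 0.8 × √(324/36) = 2.40 on 34 df, and power = 76.0%. This matches the stated 76%.

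*The same calculation with fewer outcomes:*

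| Participants with an outcome | δ | Power | Drop from 76.0% (points) | d detectable with 76% power |
|---|---|---|---|---|
| 18 + 18 | 2.40 | 76.0% | – | 0.80 |
| 15 + 15 | 2.19 | 68.9% | 7.1 | 0.88 |
| 15 + 14 | 2.15 | 67.5% | 8.5 | 0.90 |
| 14 + 14 | 2.12 | 66.1% | 9.9 | 0.91 |

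A simulation with 400,000 replicates per row gave 76.1%, 68.9%, 67.5% and 66.2%.

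**Attrition allowance**

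- Loss covered by three extra per arm: 3/18 = 16.7%.
- Remaining after a 20% loss: 36 × 0.8 = 28.8 in total, or 14.4 per arm, against a target of 30.
- Enrolment needed to keep 15 per arm at a 20% loss: 15/0.8 = 18.75, so 19 per arm or 38 in total. The plan's 36 equals 30 × 1.2, which inflates by the loss rate instead of dividing by the retention rate.

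**How much expectation maximization could recover.** The documents give no correlation r between baseline and post-treatment MIST, so a range is assumed. Further assumptions are data missing completely at random, baseline MIST as the only auxiliary variable, and a large-sample approximation. With 14.5 outcomes per arm out of 18 enrolled, the variance of an arm mean is s² × [(1 − r²)/14.5 + r²/18], and the effective n is s² divided by that variance.

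| r | Effective n per arm | Power |
|---|---|---|
| 0.3 | 14.8 | 68.2% |
| 0.5 | 15.2 | 69.5% |
| 0.7 | 16.0 | 71.5% |
| 0.8 | 16.6 | 72.8% |

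At r = 0.9 the effective n is 1/(0.19/14.5 + 0.81/18) = 17.2 and power is 74.3%, still below 76%.

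**Precision of Cohen's d.** SE = √[(n1 + n2)/(n1·n2) + d²/(2(n1 + n2))] at d = 0.8.

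- 18 + 18: √(0.1111 + 0.0089) = 0.346; 95% half-width 1.96 × 0.346 = 0.68.
- 15 + 14: √(0.1381 + 0.0110) = 0.386; 95% half-width 1.96 × 0.386 = 0.76.

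**The case against.** The strongest defence is that the power sentence is literally true. The paragraph opens with 36 enrolled, and 76% is the right power for 36 outcomes. On that reading the power point is an omission, and only the attrition allowance is an arithmetic slip, worth about one completer. This is fair as a description. However, an unlabelled power figure placed directly after an attrition allowance will be read as net of attrition, and it is not.

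Three further points have some weight.

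- **The figure drives little.** Enrolment rests on the 15-per-arm rule, the stated efficacy output is Cohen's d, and Section 8.0 names no hypothesis test for the MIST. The power sentence does not name an outcome either, so linking it to the post-treatment MIST is a reasonable inference rather than the plan's own words. This limits the consequence but does not make the figure right.
- **Completers are not the planned analysis set.** Expectation maximization may be used, and the wider baseline battery could predict the outcome better than baseline MIST alone, so 73% is not an upper limit. The true loss under the planned analysis is unknown. But the method is conditional, and even a correlation of 0.9 does not bring power back to 76%.
- **Attrition need not mean a missing outcome.** Section 9.0 lets participants stop the intervention, and someone who does so without leaving the study might still be assessed at week 6. If some of the 20% are of this kind, the loss is smaller. For actual withdrawals before week 6, Section 7.0 rules out a later assessment.

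**Conclusion.** The concern holds. The 76% is correct for 36 observed outcomes and for no smaller number. At 20% loss of outcomes, power for completers is about 67% (66.1% to 67.5% in whole participants), a drop of about 8.5 to 10 points. At the 15 per arm that the extra six are meant to protect, it is 68.9%, a drop of about 7 points. The chance of missing a large effect is thus about 31% to 34% among completers, not 24%. The six added participants cover 16.7% attrition, leaving the plan about one completer short of 30 at 20%.

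These figures rest on d = 0.8 and on reading attrition as loss of the post-treatment outcome. Expectation maximization would narrow the gap by an amount the documents do not allow one to fix. For a feasibility pilot the effect is modest: the interval around d widens from about ±0.68 to ±0.76. It should still be corrected, because it is a headline design figure that the plan's own attrition assumption does not support.

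**What to change.** Keep enrolment at 36 and replace the allowance and power sentences in Section 8.0 with wording such as:

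> Enrolling 36 participants (18 per arm) retains 15 per arm if attrition is about 17%, and about 29 participants in total if it is 20%. For d = 0.8 and a one-tailed 5% independent t-test, power is 76% with no attrition, about 69% with 15 completers per arm, and about 67% with 29 completers (15 + 14).

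This also states the effect size that the plan leaves as large. The cost is wording only: enrolment, randomization and analysis do not change, though the stated power becomes less favourable.

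Raising enrolment is not needed for the pilot's purpose and would not be a small change. Going to 38 would keep 15 per arm at 20% loss but give only about 69% power (15.2 per arm). Holding 76% at 20% loss would take 23 per arm (23 × 0.8 = 18.4, power 76.9%).

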4.0 Enrollment/Randomization

The study will be conducted at the Mandell Center for MS (Mandell Center), which provides comprehensive care to persons with MS, thus allowing for easier recruitment of the intended patient population. As of December 31, 2019, 3,134 unique patients have been seen at the Mandell Center ([name], personal communication, January, 23, 2020). Similar to the general MS population³¹, our patient population has more women than men ([name], personal communication, November 16, 2017). Patients range from age 18 to 88 (mean: 50.23 years) and are, on average, moderately disabled, as measured by the Expanded Disability Status Scale (EDSS) (mean: 3.8; range: 0-8.5)³² ([name], personal communication, November 16, 2017).

Participants will be primarily recruited through the *Recruitment Pool for Studies at the Mandell Center for Multiple Sclerosis* (IRB# MSH-19-48), an ongoing project where PwMS opt-in to be contacted about research opportunities at the Mandell Center. To date, there are over 400 individuals who have agreed to be contacted about research studies being conducted at the Mandell Center. Potential participants will be contacted via email (with an IRB-approved recruitment letter) or via phone call. Recruitment flyers will also be posted in the Mandell

Center, made available to staff, and distributed to the community. All recruitment materials will list the inclusion criteria and contact information. Prior to enrollment in the study, potential participants will be screened over the phone for the inclusion criteria. As the study is primarily being conducted via telehealth, we plan to have participants have minimal on-site visits.

After completion of the baseline evaluations, participants will be randomized 1:1 into the treatment or control group, stratified by age and gender. A research assistance not involved in the data collection will be responsible for treatment allocation. This study will be single masked: different study personnel will be involved in the assessment and treatment portions of the study.

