At the baseline and post-treatment assessments, participants will be completing a battery of neuropsychological measures. These are protected, copyrighted measures that are being purchased under [name] license and will only be administered, scored, and interpreted by [name]. All of these measures are standard neuropsychological measures frequently used in routine neuropsychological assessments. The measures being given are noted in the attached document **TPMI Measure Checklist**. No diagnoses of cognitive impairment will be made after either assessments, as this study is not part of clinical care.

As these measures cannot be scanned and uploaded due to copyright restrictions and accordance with the American Psychological Association's ethics code, details are provided below on each measure:

Test of Premorbid Functioning (TOPF)⁴⁰: is a measure of premorbid functioning. The participant reads aloud a list of words, which increase in complexity. The participant will only complete this measure at baseline. If a participant completed the TOPF in another study (i.e., MSH-21-09), they will not repeat the TOPF in this study as their scores are expected to remain stable over time.

Memory for Intentions Test (MIST)^{28,29}: is an eight-task objective measure of PM. The participant is given eight tasks over the course of the test at differing times, to which they must give a response at either a designated time or after a certain cue. The tasks in the MIST are meant to mimic everyday activities (e.g., recalling what medications they take). The participants are given one additional task with a 24-hour delay, in which they would call a secure research line [contact]) and report how many hours of sleep they received the night before. The MIST will be given at baseline and post-treatment, and the total score will be used to calculate the preliminary effect size. To reduce learning effects, different versions of the MIST will be given at baseline and post-treatment.

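### Allocation is stratified by age and gender but no analysis in section 8.0 uses them; an adjusted efficacy model with an interval would be a free improvement

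*Combined protocol and SAP*

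**What the plan says.** Section 4.0 states that "participants will be randomized 1:1 into the treatment or control group, stratified by age and gender". It gives no age cut-points, number of strata, block size or allocation method.

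Section 8.0 does not return to these factors. The power statement is "This sample size is adequate to detect a large effect size with 76% power and 5% significance on a one-tailed independent t-test". For the participant ratings, "independent t-tests or Mann-Whitney U tests will be run for treatment credibility, expectancy, and satisfaction". Adherence is summarized descriptively. For efficacy, a Cohen's d "effect size will be computed for the group difference and will be used to inform a definitive clinical trial", under intent-to-treat with EM for missing values if a missing-values analysis supports it. Section 5.0 names the outcome: "The MIST will be given at baseline and post-treatment, and the total score will be used to calculate the preliminary effect size". No model, covariate, test or confidence interval is given for the MIST or the PDQ.

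**The concern.** Stratifying with balance inside each stratum removes between-stratum variation from the difference between arms. The ordinary two-sample standard error does not know this and still counts that variation. If age or gender predicts the score, an unadjusted standard error would overstate the uncertainty, and a test or interval built on it would be conservative. Putting the stratification factors in the model gives the design credit for its balance.

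Drop-out is a second reason. The plan allows for 20% attrition, and section 7.0 ends research appointments once a participant withdraws, so the post-treatment MIST of those participants is lost. If losses differ by age or gender between arms, an unadjusted d can absorb the imbalance that stratification was meant to prevent. That d is the Aim 2 result carried forward to the definitive trial.

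**Working it through.** **Inputs.** From section 8.0: 18 per arm, one-sided 5%, independent t-test, stated power 76%. Assumed: d = 0.8 for a large effect (no number is given), and R², the share of MIST variance explained by age and gender, from 0 to 0.3.

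**1. The plan's own figure.** Noncentrality = d·√(n/2) = 0.8 × √9 = 2.4, with 34 degrees of freedom. The one-sided 5% noncentral t power is 0.760. The stated 76% reproduces.

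**2. Adjusted model, ideal balance.** Residual SD = √(1 − R²), so noncentrality = 2.4/√(1 − R²) on 32 degrees of freedom. The unadjusted standard error is too large by the factor 1/√(1 − R²).

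| R² | Power, adjusted | SE factor, unadjusted | 95% CI half-width (SD units), unadjusted → adjusted |
|---|---|---|---|
| 0 | 0.759 | 1.00 | 0.677 → 0.679 |
| 0.1 | 0.797 | 1.05 | 0.677 → 0.644 |
| 0.2 | 0.837 | 1.12 | 0.677 → 0.607 |
| 0.3 | 0.877 | 1.20 | 0.677 → 0.568 |

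**3. Simulation with realistic balance.** Assumed: four strata (two age groups by gender), 75% women, even age split, permuted blocks of 4, 8,000 trials per setting. SDs, standard errors and size are from the runs with no effect; power is at d = 0.8.

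| R² | Mean unadjusted SE / true SD of the unadjusted difference | One-sided size, plain t-test | Power, plain | Power, adjusted |
|---|---|---|---|---|
| 0 | 0.3310/0.3313 = 1.00 | 5.0% | 0.75 | 0.75 |
| 0.1 | 0.3325/0.3191 = 1.04 | 4.4% | 0.77 | 0.79 |
| 0.2 | 0.3329/0.3006 = 1.11 | 3.1% | 0.77 | 0.83 |
| 0.3 | 0.3325/0.2874 = 1.16 | 3.0% | 0.79 | 0.88 |

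The Monte Carlo standard error on power is about √(0.77 × 0.23/8000) = 0.005. Across comparable simulations the excess in the standard error was roughly 2–5%, 7–11% and 12–16% at R² of 0.1, 0.2 and 0.3; one run with blocks of 2 reached 17% at R² = 0.3.

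**4. Does the estimate itself change?** Hardly, with complete data. The true SD of the unadjusted and adjusted differences was 0.319 and 0.318 at R² = 0.1, and 0.287 and 0.280 at R² = 0.3.

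**5. Without blocking within strata.** The plain test is not conservative (size 5.0% to 5.5%). Adjusting moves power from 0.751 to 0.728 at R² = 0, a loss of 2.3 points, and from 0.75 to 0.76, 0.81 and 0.85 at R² of 0.1, 0.2 and 0.3.

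**6. Drop-out.** Random loss of one sixth of participants produced no bias. A deliberately unfavorable illustration put losses of 30% and 3% in opposite age groups by arm. A true difference of 0.80 then appeared unadjusted as 0.87, 0.92 and 0.94 at R² of 0.1, 0.2 and 0.3, with one-sided size of 6.6%, 7.8% and 8.5%. The adjusted estimate stayed near 0.80 and its size near 5%. The rise depends on how much of R² is due to age. It shows a mechanism and is not a forecast.

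**The case against.** The case for leaving the plan alone is substantial, and most of it stands.

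- The efficacy deliverable is a point estimate, and step 4 shows that it is almost as precise unadjusted. A reader might infer that the precision bought by stratifying is thrown away. It is not: the balance already sits in the plain difference, and only the credit for it in a standard error, test or power figure is lost.
- A reader might infer that the planned intervals are too wide, or that every comparison in section 8.0 is a plain two-sample one. The documents support neither. No interval or test is planned for the MIST or PDQ, and adherence is descriptive.
- The excess width needs both a prognostic effect of age or gender and balance within strata. The documents give no association with the MIST and do not mention blocking.
- Any error with complete data is on the conservative side, in a pilot with no confirmatory test.
- Extending the model to credibility, expectancy and satisfaction would be a preference. Aim 1 judges these against a threshold of 7 out of 10, and nothing suggests that age or gender predicts them.

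What remains is that the factors chosen for the design are absent from an efficacy analysis that has no stated model. Using them needs no new data and costs little if they turn out not to matter. EM does not clearly cover the drop-out risk, because it is conditional and no variables are named for it.

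**Conclusion.** The point holds in a limited form, as a free improvement of minor to moderate weight for a 36-person pilot. The stated 76% power is not in error. Given balance within strata and R² of 0.1, 0.2 or 0.3, an unadjusted standard error would be modestly too large (step 3), and adjusting would raise power at d = 0.8 from about 0.77, 0.78 and 0.79 to about 0.79, 0.84 and 0.88. At R² = 0 adjusting costs about half a point under blocking and up to about 2.5 points without it. Adjusting also guards against age or gender imbalance from uneven drop-out, though nothing in the documents shows that such drop-out is to be expected. All these sizes rest on an assumed R², an assumed d and, for the standard error, an assumed blocking scheme.

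**What to change.** Add to section 8.0: *Aim 2 group differences (MIST, PDQ) will be estimated from a linear model with arm, age (continuous) and gender, and the adjusted mean difference will be reported with a 95% CI. Cohen's d will be the adjusted difference divided by the pooled unadjusted within-arm SD.*

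The choice of SD matters. Dividing by the model's residual SD would inflate d by 1/√(1 − R²), that is by about 5%, 12% or 20% at R² of 0.1, 0.2 or 0.3, and the definitive trial would be sized on the inflated value.

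Leave the tests for credibility, expectancy and satisfaction, and the 76% power statement, as they are. The cost is two sentences and two degrees of freedom, with no new data.

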5.0 Study Procedures

Baseline and Post-Treatment Assessments

All participants (n = 36) will complete a baseline (week 1) and a post-treatment cognitive evaluation (week 6). These assessments will be conducted by [name], a licensed neuropsychologist and research scientist at the Mandell Center with experience conducting cognitive-focused studies. Both the PM (active) and Education (control) groups will be receiving the same assessment measures at the same time points (see **Figure 1** and **Figure 2**).

Questionnaires:

Demographics will be collected, including age, gender, race/ethnicity, disease duration, MS subtype, level of education, living situation and location, insurance type, and current DMT usage. Adherence to DMTs will be assessed with a single item, ("People often have difficulty taking their medications for one reason or another. How many times have you missed taking your DMT in the past month?")³³. Items about other functional tasks, such as driving, will be asked. Level of disability will be assessed using the Patient Determined Disease Steps (PDDS)³⁴⁻³⁷ and MS symptoms will be measured using the SymptoMScreen³⁸. All of these measures are included in the document **TPMI Baseline Questionnaires**.

At baseline and post-treatment, both groups will complete the Perceived Deficits Questionnaire (PDQ)³⁰, a 20-item self-report measure of cognitive functioning. While we will be primarily looking at subjective PM with the PM subscale, we will also collect participants' reports on the three additional subscales (retrospective memory, attention, and planning/organization). This measure has been uploaded in the document **PDQ for TPMI**.

At baseline and post-treatment, both groups will be given a Prospective Memory Diary³⁹ (document name: **Memory-Diary**). During the assessment sessions, [name] and the participant will identify five tasks and the participant will fill out how they carried out the task during the week (i.e., Week 1 following the baseline assessment and Week 6 following the post-treatment assessment). These Prospective Memory Diaries will be mailed back or scanned and emailed back to the research team after they are completed. Participants will be provided with a

pre-stamped return envelope, as well as a secure research email address ([contact]) if they prefer to scan and email.

Neuropsychological Assessments:

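### The Cohen's d for efficacy has no stated baseline adjustment, score form or standardising SD, although baseline MIST is scheduled for everyone before randomization

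*Combined protocol and SAP*

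**What the plan says.** All references are to the combined protocol and SAP.

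- **Section 8.0, Statistical Considerations.** Preliminary efficacy is analysed by intent-to-treat, with EM if a missing-values analysis supports it. Then Cohen's d: the "effect size will be computed for the group difference and will be used to inform a definitive clinical trial". The tests in that paragraph are for credibility, expectancy and satisfaction. A t-test that could apply to efficacy appears only in the sample-size paragraph, where 36 participants give 76% power for a large effect at "5% significance on a one-tailed independent t-test".
- **Section 2.0, Aim 2.** The MIST is the primary outcome, "which will be used to generate a preliminary effect size estimate for a future trial". The hypothesis speaks of improvement in the treatment group. The PDQ PM subscale is a secondary outcome.
- **Section 5.0, MIST entry.** "The MIST will be given at baseline and post-treatment, and the total score will be used to calculate the preliminary effect size". To limit learning effects, "different versions of the MIST will be given at baseline and post-treatment".
- **Section 5.0, Questionnaires.** "At baseline and post-treatment, both groups will complete the Perceived Deficits Questionnaire".
- **Section 4.0.** "After completion of the baseline evaluations, participants will be randomized 1:1 into the treatment or control group, stratified by age and gender".

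No section names a covariate, a model, the week-6 or change score, or the SD that standardises d.

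**The concern.** Two things are left open.

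First, the estimate is not fully defined. Two MIST totals per participant allow at least three readings of the group difference: week-6 score, change score, or baseline-adjusted week-6 score. Each can be divided by more than one SD. These give different values of d from the same data, and d is the figure the plan intends to carry into a definitive trial.

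Second, baseline MIST is a valid covariate, because it is scheduled for everyone and measured before allocation, yet the plan does not say that it will be used. With 18 per arm, chance baseline imbalance is sizeable. If baseline and week-6 scores are at least moderately correlated, an unadjusted estimate gives away precision that costs nothing to keep.

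**Working it through.** **Inputs.** From section 8.0: 18 per arm enrolled, 15 per arm before the attrition allowance, 5% one-tailed, 76% power. Assumed, because the documents give no value: d = 0.8 for a large effect; baseline to week-6 correlation r = 0.3 / 0.5 / 0.7; normal scores with equal SD at both visits. Differences are in raw SD units.

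**1. The plan's own figure.** Two-sample t-test, 34 df, noncentrality 0.8 × √(18/2) = 2.4, one-tailed 5%: power 76.0%. The stated 76% reproduces. At 15 per arm it is 68.9%.

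**2. Precision** (n per arm).
- Week-6 score: SD of the difference = √(2/n) = √(2/18) = 0.333.
- Change score: √(2/n × 2(1 − r)) = 0.394 / 0.333 / 0.258.
- ANCOVA on baseline: √(2/n × (1 − r²) × (1 + 1/(2n − 4))). The last factor, 33/32 at n = 18, is the price of estimating the slope. Result: 0.32 / 0.29 / 0.24.
- Break-even with the week-6 score: (1 − r²) × 33/32 = 1, so r² = 1/33 and r = 0.17. At 15 per arm, r² = 1/27 and r = 0.19.

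**3. Power on the t-test in the sample-size paragraph** (200,000 simulated trials per cell for ANCOVA and change score).

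| Per arm | Week-6 score | Change score, r = 0.3 / 0.5 / 0.7 | ANCOVA, r = 0.3 / 0.5 / 0.7 |
|---|---|---|---|
| 18 | 76% | 63 / 76 / 92% | 78 / 85 / 94-95% |
| 15 | 69% | 56 / 69 / 87% | 71 / 78 / 90% |

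At 18 per arm, ANCOVA power is about 76% at r = 0.2 and 75% at r = 0.1 and at r = 0: a loss of about 1 point when r is near zero.

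**4. Contrast and divisor.** With the same raw SD, week-6 d minus change d is the standardised chance difference at baseline, whose SD is 0.333 at 18 per arm. The chance that it is at least 0.2 in size is 2 × (1 − Φ(0.2/0.333)) = 2 × (1 − Φ(0.6)) = 55%, whatever r is. Simulation gives 55% at 18 per arm and 59% at 15. Any reduction of imbalance by the age and gender strata is ignored.

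The divisor matters separately. A true difference of 0.5 raw SD, divided by the SD of change, is 0.5/√(2(1 − r)) = 0.42 / 0.50 / 0.65. If such a d were read as a week-6 d, a main trial with 90% power at two-sided 5% would get 118 / 85 / 51 per arm, against 85 for the true 0.5.

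**5. Bias.** The raw mean difference is unbiased with or without adjustment. Cohen's d is slightly too high in small samples: the factor at 34 df is 1/(1 − 3/(4 × 34 − 1)) = 1.023, so a true 0.80 averages 0.80 × 1.023 = 0.818. Simulation gives about 0.82 both unadjusted and adjusted on the raw pooled SD.

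**6. Use for sizing.** Simulated pilots with true d = 0.5 and r = 0.5; the main trial is sized from each positive pilot d for 90% power at two-sided 5% and analysed unadjusted. True power falls below 80% in 44% of cases with the unadjusted d and 42% with the adjusted d at 18 per arm (46% and about 44% at 15).

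**The case against.** The strongest reply is that this is a feasibility pilot whose efficacy aim is preliminary, and that the stated purpose of d is to inform a later trial. For that purpose adjustment barely helps (44% against 42%). The power gains belong to a test that the efficacy analysis paragraph does not list. The precision gain rests wholly on r, is negligible at r = 0.3, and may be reduced by the alternate MIST versions. The normal, equal-variance model is untested for a total built from eight tasks. ANCOVA is also not the only defensible choice.

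Most of this stands. It is why precision rather than power is the measure of the gain here, and why this is an improvement and not an error. It does not close the specification gap, which is independent of r.

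Four stronger readings are tempting and are not supported:

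- *That the plan rules out adjustment.* It is silent. Aim 2's mention of improvement may hint at change from baseline, and EM could draw on baseline MIST for missing week-6 scores, but neither defines the estimate.
- *That the unadjusted estimate is biased, or that adjusting cures the bias in d.* The raw difference is unbiased, and the roughly 2% excess in d is the same either way.
- *That the 76% is wrong.* It is correct for its own test.
- *That the more favourable d would be picked after the data are seen.* Nothing in the documents suggests this. The 55% shows only that the choice matters, and it applies to two d values on the same raw SD.

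**Conclusion.** The gap is real and worth closing, as a cheap improvement. Section 8.0 leaves the adjustment, the score form and the divisor of the primary efficacy estimate unstated, and no other section supplies them. A concrete better method is available from data already scheduled.

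The size of the precision gain is conditional on r: slight at 0.3, about 12% off the SD of the estimate at 0.5 (0.293 against 0.333), about 27% at 0.7 (0.242 against 0.333), and a small loss below about 0.17. The need to define the contrast and divisor in advance does not depend on r.

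A reader might infer that ANCOVA would make the pilot d a safe basis for sizing the definitive trial. It would not: at this sample size the point estimate remains too uncertain with or without adjustment.

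**What to change.** In section 8.0, state that:

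1. Week-6 MIST total is compared between arms by ANCOVA adjusted for baseline MIST, and the PDQ PM subscale likewise for its own baseline, keeping the intent-to-treat and EM provisions.
2. d is the adjusted mean difference divided by a raw SD named in advance (unadjusted pooled, or baseline). The residual SD should not be used, since it inflates d.
3. d is reported with a 95% CI, together with the pilot SD and the baseline to week-6 correlation, and these are carried into the main-trial sizing instead of the point estimate alone. As a guide, the unadjusted 95% CI around an observed d of 0.5 is -0.17 to 1.16 at 18 per arm and -0.23 to 1.22 at 15.

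Age and gender, as stratification factors, are optional covariates. If neither is prognostic, adding both brings power at 18 per arm to 76 / 83 / 93% at r = 0.3 / 0.5 / 0.7, and 72-73% at r = 0.

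The cost is analysis wording and one degree of freedom for the baseline score. No extra visits, measures or participants are needed. The wording should be settled before outcome data are seen.
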